creatinine, follicle stimulating hormone [FSH; at pre-study for postmenopausal women only]), and urinalysis (pH, specific gravity, protein, glucose, ketones, white blood cells, red blood cells, leucocyte esterase, urobilinogen, bilirubin, culture where applicable) pre-study, prior to the first dose, weekly, at End of Dosing, and at Follow-Up. Serology for Hepatitis B, C and HIV and urine drug of abuse at screening only.

⁷ Performed pre-study, pre-dose and 30 minutes, 1, 2, 4 hours (and 6, 8, 12 and 24 hours on Day 1) post-dose, at end of study dosing, and at follow-up.

⁸ Screening (serum); otherwise, urine dipstix, confirmed with serum hCG if equivocal.

⁹ EDSS will be assessed at Screening, Baseline, End of Dosing and at other timepoints when clinically indicated by neurological examination

¹⁰ 3 x 10 mL whole blood sample collected pre-each dose

¹¹ 3 x 10 mL whole blood sample collected 24 hours post each dose

Version 5

| | Pre- | Clinic Visit (Cycle 1) | | | | | | | | | |
|--|----------------|------------------------|-----|----------------|---|----------------|----|----------------|----|------------------|--|
| | Study | | Day | | | | | | | | |
| | (-28 | 1 | 2 | 8 | 9 | 15 | 16 | 22 | 23 | Early Discharge: | |
| Study Procedures | days) | Baseline | | + 1 day | | + 1 day | | + 1 day | | All Subjects | |
| Medical history | Х | | | | | | | | | | |
| Physical examination | X ¹ | X ^{2,3} | | X ² | | X ² | | X ² | | X ¹ | |
| Neurological examination ⁴ | x | X ³ | | | | | | | | x | |
| Ophthalmologic examination ⁵ | x | | | | | | | | | x | |
| Inclusion/ exclusion criteria | х | | | | | | | | | | |
| Informed consent | Х | | | | | | | | | | |
| Body weight | Х | X ³ | | | | | | Х | | Х | |
| Vital signs ⁶ | Х | Х | | Х | | Х | | Х | | X | |
| Clinical laboratory testing ⁷ | x | X ³ | | х | | х | | х | | х | |

Table 3 Schedule of Events (DC Phase – Cycle 1)

¹ Thorough examination pre-study and at end of study dosing.

² Symptom-directed examination weekly during the first cycle, once each subsequent cycle, and at follow-up.

³ If pre-study assessment was performed within 3 days prior to baseline, assessments do not need to be repeated prior to initiation of dosing.

⁴ Neurological examination will be conducted at screening, baseline and end of dosing, and at other timepoints when indicated by history and adverse events.

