7.6 ECG and Echocardiogram

A 12-lead ECG will be recorded for all subjects at screening, pre-dose and 30 minutes, 1, 2 and 4 hours (and 6, 8, 12 and 24 hours on Day 1) post-dose in Cycle 1, at the end of study dosing, and at follow up. For DC phase subjects only, ECG will be recorded predose and 4 hours post dose on each subsequent dosing day.

An ECG will be recorded after the subject has been lying supine for at least 5 minutes. The date and time the ECG was recorded, as well as the protocol and subject identification details should be recorded on the printout.

The following parameters will be recorded in the CRF: heart rate, PR, QRS, QT, QT_{cF} as well as any abnormality in rhythm or wave morphology.

In the DC phase only, subjects will undergo echocardiography during screening.

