12.2 Adverse Events and Laboratory Abnormalities

12.2.1 Clinical Adverse Events

An Adverse Event is any untoward medical occurrence in a patient or clinical investigation subject administered a pharmaceutical product and which does not have to have a causal relationship with this treatment. An Adverse Event can therefore be

Version 5

any unfavourable and unintended sign, symptom, or disease temporally associated with the use of a medicinal product, whether or not considered related to the medicinal product. Pre-existing conditions that worsen during a study are to be reported as Adverse Events.

An adverse event is any adverse change from the subject's baseline condition, including any clinical or clinically significant laboratory test value abnormality that occurs during the course of the clinical study after the experimental drug has been utilized, whether the adverse event is considered related to the treatment or not.

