14.3.1.2 Baseline Values

All assessments on Day 1, before the first dose of the study drug, will be considered as Baseline. If the value at Baseline is missing, the last value from the Screening visit will be used as Baseline. If there are multiple Baseline assessments, the most recent one will be used for analysis.

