14.5.3.3 Clinical Laboratory Assessments

Summary statistics will be presented for Baseline laboratory measurements, including hematology, chemistry, coagulation, and urinalysis. Normal ranges for the laboratory parameters will be provided by the laboratory which performed the assessments. All normal ranges will be standardized and results will be reported in standard units. The tables will include summary statistics for the Baseline assessments and the changes from Baseline to each subsequent timepoint of measurement. Shift tables will be generated for each laboratory parameter (except urinalysis), showing the transitions

Version 5

from Baseline assessment to normal (within normal range), low, or high value on each subsequent timepoint. A listing of subjects with abnormal laboratory assessments will be presented.

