14.5.3.5 Electrocardiogram (ECG) Findings

ECG findings, including changes from baseline to each subsequent timepoint, will be summarized for each dose level using descriptive statistics. The number and percentage of subjects with clinically significant abnormal ECG findings at any visit will be tabulated.

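### The count of clinically significant ECG abnormalities has no start point, so findings present before the first dose are counted with those that appear on MIS416

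*Protocol*

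**What the plan says.** Section 14.5.3.5 plans two ECG outputs. The first is tied to baseline: "ECG findings, including changes from baseline to each subsequent timepoint, will be summarized for each dose level using descriptive statistics". The second is a count of subjects and is not: "The number and percentage of subjects with clinically significant abnormal ECG findings at any visit will be tabulated".

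Section 7.6 sets the schedule: "A 12-lead ECG will be recorded for all subjects at screening, pre-dose and 30 minutes, 1, 2 and 4 hours" after dosing, with further recordings on Day 1. Footnote 7 to Table 2 agrees ("Performed pre-study, pre-dose and 30 minutes, 1, 2, 4 hours"), and the corresponding footnote to Table 3 has the same wording for the dose-confirmation phase. Section 14.3.1.2 defines the reference value: "All assessments on Day 1, before the first dose of the study drug, will be considered as Baseline". If that value is missing, the last screening value is used.

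Laboratory data are handled differently. Section 14.5.3.3 says: "Shift tables will be generated for each laboratory parameter (except urinalysis), showing the transitions" from Baseline to low, normal or high at each later timepoint. No such table is named for ECG.

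**The concern.** A safety rate from a single-arm study is useful only if it separates what the subject brought in from what appeared on the drug. As worded, this count does not. A clinically significant finding seen only at screening or before the first dose scores the same as one that emerges after an infusion. A subject abnormal at baseline scores once whether the ECG later resolves, stays the same or worsens.

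The synopsis and section 7 list changes in ECGs among the assessments for the primary safety endpoint, and a count that includes pre-drug recordings does not measure change. It is also the only ECG-specific categorical rate the protocol names, so it is likely to be read as the rate on MIS416.

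Cardiac findings deserve a clean table here. Section 1.4.4 attributes the three high-dose deaths or sacrifices in the 26-week rabbit study to cardiac myofibre degeneration and necrosis. Echocardiography is scheduled only at screening and only in the dose-confirmation phase (section 7.6), so ECG is the main scheduled cardiac test during treatment.

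**Working it through.** The protocol states no figure to reproduce for this point. The check has three parts.

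**1. Does any other rule remove the pre-dose ECGs?**
- Section 14.3.1.1 uses nominal visits and keeps only unscheduled assessments out of tabulations by visit. Screening and Day 1 are scheduled.
- Section 14.2.2 restricts the safety population to subjects who received drug. That restricts subjects, not timepoints.
- Footnote 3 to Tables 2 and 3 waives some Day 1 assessments if they were done within the previous 3 days, but it is not attached to the ECG row.

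So both recordings stay in.

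**2. How many scheduled ECGs precede the drug?** (Section 7.6; Tables 2 to 4)

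| Recording | Dose escalation | Dose confirmation, 3 cycles |
|---|---|---|
| Screening | 1 | 1 |
| Day 1 pre-dose | 1 | 1 |
| Day 1 post-dose (30 min, 1, 2, 4, 6, 8, 12, 24 h) | 8 | 8 |
| Days 8, 15, 22 (pre-dose, 30 min, 1, 2, 4 h) | 3 × 5 = 15 | 3 × 5 = 15 |
| Cycles 2 and 3: 8 dosing days (pre-dose, 4 h) | – | 8 × 2 = 16 |
| End of dosing | 1 | 1 |
| Follow-up | 1 | 1 |
| **Total** | **27** | **43** |
| Before any drug | 2 | 2 |

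This leaves 27 − 2 = 25 and 43 − 2 = 41 recordings after the first dose. The ratios describe the schedule. They do not measure bias, because the table counts subjects rather than recordings.

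**3. What does one affected subject do to the rate?** A subject with a pre-existing abnormality and no new or worsened finding adds 1/n, while the emergent rate gains nothing.
- Cohort of 3: 1/3 = 33.3%
- Cohort of 6: 1/6 = 16.7%
- Dose-confirmation group of 15: 1/15 = 6.7%

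The documents do not give the prevalence p of a clinically significant ECG abnormality among enrolled subjects. For assumed values only, the chance of at least one such subject is 1 − (1 − p)^n:

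| Assumed p | n = 3 | n = 6 | n = 15 |
|---|---|---|---|
| 2% | 5.9% | 11.4% | 26.1% |
| 5% | 14.3% | 26.5% | 53.7% |
| 10% | 27.1% | 46.9% | 79.4% |

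**The case against.** The best counter-argument is that table-level rules of this kind usually sit in the SAP, which is not at hand, and that nothing in section 14.5.3.5 is false. A SAP may indeed narrow the wording. But the protocol does not leave the rule open here. It states one, and that rule is too broad. Nor would an unwritten understanding that safety counts start after the first dose be enough, because an abnormality that persists from baseline would still count.

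Second, emergent ECG abnormalities are captured elsewhere. Section 12.2.1 defines an adverse event as an adverse change from the subject's baseline condition after the drug has been used, and adds: "Pre-existing conditions that worsen during a study are to be reported as Adverse Events". A new clinically significant ECG finding fits that definition, and section 14.5.3.2 tabulates adverse events by dose cohort. The first sentence of 14.5.3.5 is also tied to baseline. All of this stands and reduces the consequence, but it does not correct the percentage in this table.

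Third, entry rules limit the problem. Exclusion 11 removes symptomatic dysrhythmias requiring treatment and persistent QTcF prolongation. Exclusion 10 covers uncontrolled heart failure and recent cardiac events, exclusion 12 covers echocardiographic abnormalities in the dose-confirmation phase, and exclusion 18 leaves other conditions to the investigator's judgement. This also stands. The criteria reduce the number of affected subjects without ensuring it is zero.

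Finally, the error can only overstate the rate, which is the cautious direction for safety. That is true. Even so, an inflated figure in a cohort of 3 can suggest a dose-related signal that is not there.

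**Conclusion.** The point holds, with low materiality. Read as written, the count in section 14.5.3.5 mixes pre-existing with treatment-emergent abnormalities. It rests on the literal wording, on the two pre-dose ECGs scheduled for every subject, and on no other section taking them out.

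If one affected subject is enrolled, the distortion is 33, 17 or 7 percentage points in groups of 3, 6 or 15. If none is, it is zero. Which applies cannot be told from the documents.

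Only the reporting of this table is affected. The MTD and dose escalation depend on DLTs, which must be judged at least possibly drug-related (sections 4.3 and 4.4), and the study has no hypothesis test (section 14.4.2).

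**What to change.** Replace the last sentence of section 14.5.3.5 with wording such as: *The number and percentage of subjects with a clinically significant ECG abnormality that is new or worsened versus Baseline, at any recording after the first dose, will be tabulated by dose level. Abnormalities present before the first dose will be shown separately.* Baseline keeps its section 14.3.1.2 meaning.

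A shift table from Baseline to the worst post-dose ECG category would do the same job and would bring ECG into line with the laboratory data. Changing the scope only to post-dose visits would not be enough, for the reason given above about persisting abnormalities.

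The cost is one sentence and one table. All the recordings, including the pre-dose reference, are already scheduled.

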14.5.3.6 Radiological Findings

Radiological (MRI) findings, including changes from baseline to each subsequent timepoint, will be summarized at each dose level for the following parameters:

- Gadolinium-enhancing lesions (number and volume)
- Total T2 lesion volume
- Brain parenchymal fraction

14.5.4 Analysis of Clinical Status

Analyses of clinical status endpoints will be conducted on the CS population. Summary statistics will be presented for baseline measurements and changes from baseline at each dose level for the following:

- MSFC score
- FSS score
- SF-36 score
- EDSS score
- Self-reported and clinically confirmed clinical exacerbations

Time to EDSS (TTE) deterioration will be determined as follows:

Date of first of two confirmed deteriorations from baseline minus Date of 1^{st} Study Drug Administration + 1 day. TTE deterioration will be calculated in days, but will be reported in days or months.

Version 5

14.5.5 Analysis of Pharmacodynamics (PD)

Summary statistics for PD profiles of the subjects in each dose cohort and the total population will be presented in a separate Pharmacodynamics Report. Absolute and percent changes from baseline for each subsequent timepoint will be tabulated.

The pharmacodynamic parameters will include some or all of the following: serum IFN., IL-17, IL-6, TNFa and GM-CSF levels; PBMC expression of mRNA encoding IL-12p40, IL-12p35, IL-23p19, LTa, LTß, IFN, IL-17, GM-CSF, ROR.t, and Tbet; PBMC production of IFN, IL-17, and GM-CSF in response to stimulation with anti-CD3 and anti-CD28 ex vivo; PBMC production of IL-12p40, IL-12p70, IL-23, TNFa and IL-6 in response to stimulation with LPS/IFN ex vivo. These serum and cellular findings during the dose-escalation phase will be presented. Depending on the dose-escalation findings, a selective or comprehensive set of PD parameters will similarly be summarized for the dose-confirmation phase.

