LT leucotriene MedDRA medical dictionary for regulatory activities MDP muramyl dipeptide MOG myelin oligodendrocyte glycoprotein MRI magnetic resonance imaging mRNA messenger ribonucleic acid multiple sclerosis MS MSFC multiple sclerosis functional composite MTD maximum tolerated dose NOAEL no observed adverse effect level NOD-2 nucleotide oligomerization domain-2 natural killer NK New York Heart Association NYHA PBMC peripheral blood mononuclear cell PD pharmacodynamic pDC plasmocytoid dendritic cell PPMS primary progressive multiple sclerosis PPR pathogen molecular recognition receptor RNAi **RNA** interference RORyt orphan nuclear receptor transcription factor RP2D recommended Phase 2 dose SE safety evaluable SF-36 Short Form Health Survey – 36 questions siRNA short interfering RNAs secondary progressive multiple sclerosis SPMS **Innate Therapeutics Limited** Sponsor SRT Safety Review Team T helper 1-specific T box transcription factor Tbet TLR9 Toll-like receptor 9 TNF tumour necrosis factor World Health Organisation Drug dictionary WHODrug

Version 5

SYNOPSIS

Name of Sponsor/Company: Innate Therapeutics Limited

Name of Product: MIS416

Title of Study: MIS416-2101: A Phase 2, open-label, dose-escalation study evaluating the safety, tolerability, and pharmacodynamics of intravenously administered MIS416 in patients with chronic progressive multiple sclerosis.

Objectives:

The primary objectives of this study are:

- To determine the safety and tolerability, dose-limiting toxicities (DLTs), maximum tolerated dose (MTD), and recommended Phase 2 dose (RP2D) of intravenously (IV) administered MIS416 weekly in patients with chronic progressive multiple sclerosis (CPMS); and
- 2. To assess the pharmacodynamic (PD) effects of MIS416, including effects on serum cytokine levels and peripheral blood mononuclear cell (PBMC) associated cytokine/chemokine expression patterns.

The secondary objectives of this study are:

- To document any changes in MS clinical status occurring during the 12-week MIS416 dosing period in the dose-confirmation phase, as determined by the Multiple Sclerosis Functional Composite (MSFC), Fatigue Severity Scale (FSS), Short Form Health Survey (SF-36), and Expanded Disability Status Scale (EDSS); the frequency of clinical relapses; and signs of clinical activity on serial cranial MRI scans; and
- **2.** To evaluate, in exploratory fashion, any correlations between clinical, radiological and PD outcomes.

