Pharmacodynamic Analyses: Summary statistics will be computed and the absolute and percent change from baseline will be calculated for each subsequent measurement. Summary statistics will be computed for each collection time point, as well as by dose.

Clinical Status Analyses (DC phase only): Clinical status will be tabulated using EDSS, MSFC, FSS, and SF-36; MRI findings; and by the frequency of self-reported as well as clinically confirmed clinical exacerbations.

Version 5

CONTENTS

| 1. 1.1 | BACKGROUND AND RATIONALE Scientific Background | |
|-----------|---|----|
| 1.2 | Study Drug | |
| 1.3 | Mode of action of MIS416 | |
| 1.4 | Pre-Clinical Experience | |
| 1.7 | 1.4.1 Acute Dose Studies | |
| | 1.4.2 Repeat Dose Studies | |
| | 1.4.3 4 Week Repeat Dose Studies | |
| | 1.4.4 26 Week Repeat Dose Study | |
| 1.5 | 1.4.5 Animal Toxicology Studies Conclusions | |
| 1.5 | Clinical Experience | 29 |
| 2. | RATIONALE FOR STUDY DESIGN | |
| 2.1 | Developmental Context | |
| 2.2 | Rationale Dose-Escalation Phase | |
| 2.3 | Rationale Dose-Confirmation Phase | |
| 2.4 | Selection of Starting Dose (DE Phase) | 33 |
| 3. | OBJECTIVES OF THE STUDY | 35 |
| 4. | STUDY DESIGN | |
| 4.1 | Overview of Study Design | |
| 4.2 | Number of Subjects Planned | |
| 4.3 | Dose Escalation Phase (1 cycle only) | 36 |
| 4.4 | Dose Limiting Toxicity (DE phase only) | 37 |
| 4.5 | Dose Confirmation Phase (up to total of 3 cycles) | 37 |
| 4.6 | Intra-Subject Dose Reduction (DC phase only) | |
| 4.7 | Antipyretic Pre-Medication (DC phase only) | |
| 4.8 | Safety Review Team | 38 |
| 5. | STUDY POPULATION | |
| 5.1 | Target population | |
| 5.2 | Inclusion Criteria | |
| 5.2 | Exclusion Criteria | 39 |
| 5.4 | Concomitant Medication | 40 |
| 5.5 | Restrictions | 41 |
| 6. | SCHEDULE OF ASSESSMENTS AND PROCEDURES | 41 |
| 6.1 | Screening (Days -28 to -2) | 41 |

Version 5

| 6.2 | Treatment Period (Cycle 1) – Day 1 | 41 |
|------|--|----|
| | 6.2.1 DE Phase Subjects | 41 |
| | 6.2.2 DC Phase Subjects | |
| 6.3 | Treatment Period (Cycle 1) – Days 8, 15 and 22 (+ 1) – All Subjects | |
| 6.4 | Treatment Period (Cycles 2 – 3) – Days 1, 8, 15 and 22 (+ 1) – DC Phase Subjects O | - |
| 6.5 | Treatment Period -End of Dosing (Day 29) or Early Discharge- (7 +1 days following | |
| | dose of drug) 6.5.1 DE Subjects | |
| | 6.5.2 DC Subjects | |
| 6.6 | Follow-up (15 Days Post-End of Dosing) – All Subjects | |
| | | |
| 7. | SAFETY ASSESSMENTS | 52 |
| 7.1 | Adverse events | 52 |

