The nature of the target for MIS416 and the mechanism of action are such that following *in vivo* administration and accumulation of the drug by the reticuloendothelial system, a transient inflammatory response can be expected. Monitoring of patient serum for increased levels of pro-inflammatory cytokines demonstrates the transient nature of MIS416 immunostimulation (Figure 1-6). These findings are very important since they demonstrate that administration of a single bolus of MIS416 does not induce an uncontrolled "cytokine storm", with maximum levels of serum cytokines peaking within 24 hour post delivery, returning to baseline levels by 48 hours.

Analysis of MIS416 - treated patient blood for a sustained inflammatory response, or the occurrence of a "second wave" of inflammatory activity over a longer time period (14 days) demonstrates there is no prolonged inflammatory activity following MIS416

Version 5

dosing. This further demonstrates that MIS416 innate immunostimulation is well controlled *in vivo* (Figure 1-7).

[figure not shown]
Figure 1-6

MIS416 systemic administration induces a transient serum inflammatory cytokine response which peaks within 24 hours following administration. Blood serum was harvested and directly measured for multiple cytokine content using flow cytometry cytokine bead array methodology (Bender MedSystem)

Version 5

Figure 1-7

MIS416 therapy does not lead to the sustained induction or a "second wave "of inflammatory mediators. Peripheral blood serum was harvested from two individual healthy donors and from a patient who had received 1 mg of MIS416 7 days prior to blood sampling. Blood serum was assayed for TNF- α , IL-6 and IL-1 β levels using flow cytometry bead array methodology.

2. Rationale for Study Design

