14.4 Statistical Methods

14.4.1 General Overview and Plan of Analysis

Summary statistics will be presented to describe the analysis populations, namely, the ITT, SE, and CS populations. Tabulations will include the number of subjects, mean, standard deviation, minimum, median, and maximum for continuous variables; and/or frequency and percentage of subjects for categorical variables. Summary statistics for certain safety parameters will also be presented for the MTD population.

For all subjects, the data will be tabulated by dose cohort and for the total patient population.

All statistical analyses will be performed using SAS version 9.1 (or higher), unless specified otherwise. The use of other statistical software will not be considered a violation of the statistical analysis plan, nor require an amendment of this plan.

Version 5

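### PD, a primary objective: percent change from one Day 1 baseline should be joined by a same-dose 24 h contrast and a log-ratio summary

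*Protocol*

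**What the plan says.** The second primary objective in the Synopsis is "To assess the pharmacodynamic (PD) effects of MIS416, including effects on serum cytokine levels" and PBMC-associated expression patterns. Three statements fix how the data are summarised:

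- **Scale.** Section 14.5.5: "Absolute and percent changes from baseline for each subsequent timepoint will be tabulated". The Synopsis (Pharmacodynamic Analyses) adds: "Summary statistics will be computed for each collection time point, as well as by dose".
- **Statistics.** Section 14.4.1: "Tabulations will include the number of subjects, mean, standard deviation, minimum, median, and maximum for continuous variables".
- **Reference value.** Section 14.3.1.2: "All assessments on Day 1, before the first dose of the study drug, will be considered as Baseline".

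The sampling is paired around each Cycle 1 dose. The footnotes to the schedules of events (Tables 2 and 3) give "3 x 10 mL whole blood sample collected pre-each dose" and "3 x 10 mL whole blood sample collected 24 hours post each dose", that is, Days 1, 8, 15 and 22 before dosing and Days 2, 9, 16 and 23 after it. In Cycles 2 and 3 of the dose-confirmation phase only a pre-dose Day 22 sample is taken (Table 4). Section 1.5 describes serum cytokines after a single dose as "peaking within 24 hour post delivery, returning to baseline levels by 48 hours".

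PD results inform decisions. The Safety Review Team uses them, with safety data, after each escalation cohort (Section 4.8). If no MTD is reached, they help set the recommended Phase 2 dose (Section 4.3).

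**The concern.** Two features of this summary can mislead.

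**One baseline for every later sample.** The design collects a before-and-after pair at each Cycle 1 dose, but the named analysis uses the pair only at dose 1. For doses 2 to 4 the 24 h value is compared with a sample taken one to three weeks earlier. The figure then combines the acute response to that dose with any movement in the pre-dose level since Day 1. Whether the acute response is kept, lost or increased on repeat dosing is a natural question for weekly dosing, and no named summary isolates it.

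**Arithmetic mean of percent changes.** For positive, right-skewed measurements a low baseline can produce a very large percentage rise, while no fall can exceed 100%. The mean of individual percent changes therefore sits above zero when nothing has changed. In cohorts of 3 to 6 subjects, one low baseline can dominate that mean.

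What is at stake is the descriptive reading of activity and dose response by those who decide on escalation and, if no MTD is reached, on the recommended Phase 2 dose.

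**Working it through.** The protocol states no PD variance, correlation, assay limit or expected effect, so there is no figure of its own to reproduce. CV, ρ, s, A and D below are assumptions.

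**1. Mean percent change with no drug effect.** Let baseline Y0 and follow-up Y1 be lognormal with the same distribution, CV across subjects, and correlation ρ on the log scale. Let σ² = ln(1 + CV²). Then ln(Y1/Y0) has mean 0 and variance 2σ²(1 − ρ), so

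E[percent change] = exp(σ²(1 − ρ)) − 1.

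| CV | ρ | σ² | σ²(1 − ρ) | Expected mean percent change |
|---|---|---|---|---|
| 50% | 0.7 | ln 1.25 = 0.223 | 0.067 | +7% |
| 100% | 0.5 | ln 2 = 0.693 | 0.347 | +41% |
| 150% | 0.3 | ln 3.25 = 1.179 | 0.825 | +128% |

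The log-ratio has expectation 0 in every row.

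**2. Dependence on cohort size.** Write s² = σ²(1 − ρ), so s is the within-subject log-SD and the expected bias is exp(s²) − 1. At s = 0.3, 0.5 and 0.8 this is +9.4%, +28.4% and +89.6%. It does not shrink with n. In simulation (200,000 runs per setting, no true change) at s = 0.5, the cohort mean percent change was above zero in 64% of cohorts of 3, 74% of cohorts of 6 and 87% of cohorts of 15. A true doubling at s = 0.5 has expected mean percent change 2 × exp(0.25) − 1 = +157%, not +100%.

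**3. The median, which the protocol also tabulates.** In the same simulations the cohort median percent change was centred at 0% for n = 3 and n = 15, and at 0.4% to 7.1% for n = 6 (s from 0.2 to 1.0). It is not wholly free of skewness: averaged over cohorts of 3 at s = 0.5 it was +12%, against +28% for the mean. The mean absolute change has expectation 0 under no effect.

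**4. Reference value for the 24 h samples.** Let A be the acute fold change at a dose, and D the ratio of that dose's pre-dose level to Day 1. Against Day 1 the 24 h value reads A × D − 1; against the same dose's pre-dose sample it reads A − 1.

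| A | D | Against Day 1 | Against same-dose pre-dose |
|---|---|---|---|
| 2 | 0.80 | 2 × 0.80 − 1 = +60% | +100% |
| 2 | 1.00 | +100% | +100% |
| 2 | 1.25 | 2 × 1.25 − 1 = +150% | +100% |
| 1 | 1.25 | +25% | 0% |

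**5. Where this applies.** On Day 2 the two references are the same sample, so nothing is mixed. Days 9, 16 and 23 are affected. The pre-dose samples of Days 8, 15 and 22, and of Day 22 in Cycles 2 and 3, are properly compared with Day 1.

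**The case against.** The strongest reply is that the protocol does not rest on the mean percent change. It tabulates absolute and percent change, and the median alongside the mean. In a cohort of 3, the minimum, median and maximum are the three individual values, so an extreme ratio is visible. This stands. A reader might infer that mean percent change is the sole or main PD summary; no section says so.

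Second, drift is not hidden. Pre-dose and 24 h samples are separate rows, so the pre-dose rows show change from Day 1. With complete data, subtracting rows gives the mean acute absolute change. This also stands, but the subtraction gives neither the SD of the acute change nor the percent version, and it fails when subjects drop out between samples. A reader might infer that the whole PD analysis is confounded; only Days 9, 16 and 23 are.

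Third, Section 1.5 reports serum cytokines back at baseline by 48 hours, which argues for little carry-over a week later. That is fair for serum cytokines. The description concerns a single bolus and does not cover the PBMC mRNA and ex vivo stimulation assays.

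Fourth, scale, geometric means and the handling of results below the assay limit are ordinary content of an analysis plan or of the separate PD report that Section 14.5.5 announces. Their absence alone is no defect. The point here is narrower: the protocol names a scale and a reference value, and a better choice is available for both.

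**Conclusion.** The point holds as a modest, inexpensive improvement to a stated method, not as an error that undermines the study.

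The reference-value part needs no distributional assumption: Day 1 is the only baseline, and the within-dose pairs at doses 2 to 4 are not contrasted. How much this matters depends on how far pre-dose levels move, which the documents do not show. If they stay at the Day 1 level, the two references agree.

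The skewness part is conditional. Right skew is plausible for these assays but is not stated, and the range of +7% to +128% comes from assumed CVs and correlations. The direction holds under the lognormal model whenever there is any within-subject variation; the size is not established.

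A reader might infer that an error rate, the sample size or the dose decision is invalidated. The documents do not support that. Section 14.4.2 plans no hypothesis test, no decision rule uses percent change, and PD is weighed together with the clinical data.

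**What to change.** Add two items to Section 14.5.5:

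1. **Two named contrasts.** For each Cycle 1 dose, the 24 h sample against the pre-dose sample of the same dose (acute effect). Keep each later pre-dose sample against Day 1 (cumulative effect), including Day 22 of Cycles 2 and 3.
2. **Scale for relative change.** Geometric mean ratios with 95% confidence intervals, from log-transformed values, as the main relative-change summary by dose and time point. Show the median and individual values alongside. Mean percent change may remain in the tables but should not be used for interpretation.

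The log scale needs positive values, so the analysis plan or PD report should state how results below the assay limit are handled.

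The cost is a little wording and programming, with no new samples or visits. The drawback is wide intervals in small cohorts. At an assumed s = 0.5, the SD of the log-ratio is 0.5 × √2 = 0.707. The 95% interval is then the ratio multiplied and divided by exp(4.303 × 0.707/√3) = 5.8 for n = 3, and by exp(2.571 × 0.707/√6) = 2.1 for n = 6. For cohorts of 3 the individual values will therefore carry most of the information.
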